5.2 Pre-Hotel Check-In Visit

Visit 4

All participants will be contacted by the study team approximately 24-48 hours prior to the hotel admission. The study team will verify the following information:

- a. Inquire about any changes to the participant's medical history
- b. Study equipment (e.g., CGM) has been initiated. A new CGM sensor will be placed approximately 24-72 hours prior to the hotel session for proper warm-up.
- c. Verify with participant that the goal CGM reading at time of arrival is less than 200 mg/dL; this may require contact with the study physician prior to arrival on the day of the study visit.
- d. Bring personal insulin and glucagon to hotel session.

Should any concerns regarding medical history, pump information, or unforeseen issues arise, the admission will be cancelled for that participant at the discretion of the investigator.

Chapter 6: Supervised Hotel Fully Closed-Loop Period

Visit 5 and 6

6.1 Hotel Session

The study will be performed for about 40 hours, including two 18-hour experiment sessions, at a local hotel/rental house. Participants will use the AIDANET system in the hotel setting from the afternoon/evening of Day 1 through discharge in the morning of Day 3. They will then continue to use the system for the second At-Home Period of the study.

6.2 Qualifications and Role of the Staff

There will be at least two study staff present at all times at the study site, at least one of whom will be clinical staff (e.g., nurse, physician, nurse practitioner, physician assistant). There will be a physician at the hotel or nearby on call during the study at all times. In addition, at least one senior engineer will be on call during the entire hotel session. Participants will be remotely monitored by at least one study team member (maybe trained staff, nurse, physician, NP, or PA) using a web-based remote monitoring system that has been previously established for DiAs. The web-based remote monitoring system will display real-time insulin delivery, CGM and other system information to allow for patient safety monitoring. In addition, study team members will be trained in all protocol and Glycemic Treatment Guideline procedures. The closed-loop system will be managed by the participant with study-staff supervision if needed. Glucagon for the emergency treatment of hypoglycemia will be available on-site. Participants will be instructed to bring their own rescue glucagon, though each site will also bring emergency rescue glucagon to the study.

6.3 Hotel Session Check-In

Participants will arrive at the hotel on the first day of the hotel session. The study team will perform vital signs and inquire about any changes to the participant's medical history. Any changes to medical history will be communicated to the medical physician to ensure continued eligibility and participation.

The participant's CGM reading, and ketone concentration will be recorded. In the event that the participant's CGM reading is not between 80-250 mg/dL or ketone concentration is ≥ 0.6 mmol/L prior to initiation of the FCL system, the study physician may recommend additional insulin dosing according to the participants' usual doses. Study physician may elect to cancel participant's participation in the hotel admission if concerned about their medical safety. This participant will not be replaced.

The participant's home insulin pump will be discontinued, and the study insulin pump will be initiated. The study team will ensure the proper function of the CGM and insulin pump. The CGM used in the study is FDA-approved for the non-adjunctive measurement of blood glucose (i.e., the CGM reading can be used for insulin dosing decisions). The CGM readings will be the primary source of blood glucose values. There is no required protocol fingerstick blood glucose measurements other than at times of CGM calibration (if necessary) and if directed by the study team. Fingerstick blood glucose measurements may be taken whenever participants experience

symptoms, if the CGM glucose is suspected to be erroneous, or any time the participant would like to be reassured. Glycemic Treatment Guidelines to be used during the hotel admission are defined in section 6.6.

6.4 Study Meals

Participants will eat approximately 3 freely chosen unannounced meals per day during the supervised hotel session. Study staff will record the time the meal was eaten so that analysis of the AIDANET algorithm's performance around the mealtime may be conducted. Snacks with carbohydrates will not be allowed unless for the treatment of low blood sugars. Non-carbohydrate snacks may be allowed throughout the hotel session per investigator discretion. Blood glucose levels will be followed via CGM with interventions for glucose extremes as per the Glycemic Treatment Guidelines.

6.5 Hotel Session Activities

Participants will also be free to engage in additional low-intensity activity (i.e., walking) during the hotel admission. Study staff will accompany participants if they leave the house/hotel.

6.6 Glycemic Treatment Guidelines

Hypo- and Hyperglycemia occurring while using the AIDANET system will be managed per the following protocol during both the hotel session and At-Home Period of the trial. Glycemic Treatment Guidelines will be available for staff use during the study sessions and will be provided to participants for the At-Home Period of the study.

6.6.1 Hypoglycemia

- a. If CGM falls below 70 mg/dL at any time, confirm <70mg/dL CGM readings and potential hypoglycemia symptoms with a fingerstick blood glucose. If blood glucose confirms <70mg/dL CGM reading, hypoglycemia will be treated with oral glucose of approximately 5-15 g. Participants will be encouraged to wait 15 min prior to giving a second glucose treatment. These fingerstick checks will be performed during the hotel stay and during the home portion if the participant chooses to do so. During the hotel stay we will also recheck a fingerstick blood glucose before retreatment.
- b. If a participant experiences any symptoms of hypoglycemia (e.g., shakiness, dizziness, sweating, pallor, clumsiness, difficulty paying attention, or tingling around the mouth), then the participant should treat with oral glucose of 5-15 g. Participants will be encouraged to wait 15 min prior to giving a second glucose treatment. During the hotel portion of the study, a fingerstick blood glucose will be assessed before such treatment for symptoms and before any re-treatment.
- c. If a participant displays any signs of neuroglycopenia (e.g., lethargy, disorientation, confusion, or inappropriate behavior) or severe hypoglycemia (e.g., hypoglycemic seizure, loss of consciousness, inability to properly consume treatment)

hypoglycemia will be treated with either oral glucose or glucagon. The patient will be discharged from the study. The participant should consult with study physician to discuss next steps for broader evaluation of symptoms unrelated to hypoglycemia.

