10.2.1 Hypoglycemia Event

Hypoglycemia not associated with an Adverse Device Effect is only reportable as an adverse event when the following definition for severe hypoglycemia is met:

- The event required assistance of another person due to altered consciousness, and required another person to actively administer carbohydrate, glucagon, or other resuscitative actions.
- Impaired cognitively to the point that he/she was unable to treat himself/herself, was unable to verbalize his/ her needs, was incoherent, disoriented, and/or combative, or experienced seizure or coma. These episodes may be associated with sufficient neuroglycopenia to induce seizure or coma.
- If plasma glucose measurements are not available during such an event, neurological recovery attributable to the restoration of plasma glucose to normal is considered sufficient evidence that the event was induced by a low plasma glucose concentration.

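### Section 6.6.1 item c allows oral glucose or glucagon for a group that includes seizure and loss of consciousness, without limiting oral glucose to participants able to swallow and without an instruction to call emergency services

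*Combined protocol and SAP*

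**What the plan says.** Section 6.6.1 has three items on hypoglycemia. Items a and b deal with low readings and with symptoms; in item b, for example, "then the participant should treat with oral glucose of 5-15 g".

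Item c deals with the more serious events. It joins signs of neuroglycopenia (lethargy, disorientation, confusion, inappropriate behavior) with severe hypoglycemia, illustrated as "e.g., hypoglycemic seizure, loss of consciousness, inability to properly consume treatment". For the combined group, "hypoglycemia will be treated with either oral glucose or glucagon". It then says "The patient will be discharged from the study" and adds one contact instruction: "The participant should consult with study physician to discuss next steps for broader evaluation of symptoms unrelated to hypoglycemia".

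Section 6.6 applies these guidelines to both the hotel session and the home period. Staff have them during the sessions, and they "will be provided to participants for the At-Home Period of the study". Chapter 4 also points to section 6.6 for the guidelines used at Visit 2 and at home.

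**The concern.** Oral glucose has to be swallowed. A participant who is convulsing or unconscious cannot do that safely, and one who cannot consume treatment is by definition unable to take it. Item c names all three states and still offers the oral route without a condition. It is also the item for the most dangerous events, yet its only contact instruction concerns later evaluation of symptoms not due to hypoglycemia.

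What is at stake is the safety of a participant in a rare event, mainly at home. There the participant may be unable to act, and the person following the guideline may be a companion without clinical training.

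**Working it through.** No arithmetic applies. The check is whether item c, or any other part of the protocol, says which route to use in which participant and when to summon emergency help.

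1. **Item c.** Two states and two treatments are named, joined by an either/or. No clause ties a treatment to a state.

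2. **Could the two labels serve as the rule** (neuroglycopenia gets oral glucose, severe hypoglycemia gets glucagon)? Section 10.2.1 shows that they cannot.
   - Its definition of severe hypoglycemia includes events that "required another person to actively administer carbohydrate, glucagon, or other resuscitative actions", so assisted carbohydrate is an accepted treatment for some severe events.
   - It counts as severe a participant who "was incoherent, disoriented, and/or combative, or experienced seizure or coma", whereas item c lists disorientation under neuroglycopenia.
   - The labels therefore overlap. What should decide the route is consciousness and the ability to swallow. Grouping the two states in one item is not itself an error.

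3. **Other sections that bear on a severe event.**

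| Section | What it provides | States a route rule? | Instructs a call to emergency services? |
|---|---|---|---|
| 3.4, criterion 6 | A companion who knows emergency procedures and can reach emergency services and study staff | No; the procedures are not set out | No; it describes what the companion can do |
| 3.5, criterion 4 | Excludes recent severe events with seizure or loss of consciousness | No | No |
| 5.1 | Advice to call the study team with concerns | No | No |
| 6.2 | Clinical staff always at the hotel, team trained in the guidelines, physician present or on call, glucagon on site | No | No |
| 6.8 | Glucagon at the hotel; participants confirm that they have it at home | No | No |
| 7.2 | Automated alerts to a provider, who contacts the participant and/or companion if an alert is not resolved in good time | No; it refers back to the hypo- and hyperglycemia safety protocol | No |
| 10.2.1 | Reporting definition of severe hypoglycemia | No | No |
| 10.9.1 | Discontinuation after two severe events | No | No |

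4. **Result.** The safeguards make a severe event less likely, put glucagon within reach and bring in people who can help. None supplies the missing condition on oral glucose. Emergency services appear only in criterion 6 of section 3.4, as something the companion must be able to contact.

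**The case against.** The best defense is that item c already contains the distinguishing fact. It lists inability to consume treatment as a mark of the severe state, and nobody would sensibly give that participant something to swallow. On this reading the either/or is shorthand for matching treatment to state and leaves the choice to judgement. At the hotel this is persuasive, because trained clinical staff would make the choice. It is weaker at home, where the same section is the guideline and a companion may have to choose. A rule for the most dangerous events should not depend on the reader supplying its key condition.

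A second defense is that the handout given to participants may already state the condition. That is possible; the handout is not among the documents. The point is therefore limited to the wording of the protocol.

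A third is that section 7.2 brings a licensed provider into contact with the participant or companion. That stands as mitigation. However, the contact follows an alert that has not resolved, so it may come after the first treatment decision.

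A reader might infer that the protocol directs staff or companions to put glucose in the mouth of an unconscious participant, or that home users will be misled. The documents do not support either reading. Item c permits a choice and does not prefer the oral route, and the text that participants receive has not been seen. Nor should the number of examples in item c be turned into a risk: they are illustrations, not event frequencies.

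**Conclusion.** The point holds as a gap in the wording of a safety instruction. Item c lets the oral route stand for states in which it is unsafe, and the protocol nowhere says when glucagon is required or when to call for emergency help.

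Its practical weight is small. The safeguards make harm unlikely. The protocol gives no severe-event rate, and the chance that item c would be misapplied cannot be estimated from it, so no probability is offered. Statistical validity is not in question.

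The conclusion rests on two premises: that oral glucose is unsafe in someone who cannot swallow, and that the home guidelines follow section 6.6, as Chapter 4 says. If the handout already carries the condition, the remaining task is to bring the protocol into line with it. This is a cheap improvement, not a flaw in the design.

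**What to change.** Reword only the treatment sentence of item c, for example: *hypoglycemia will be treated with oral glucose if the participant is conscious and able to swallow safely; otherwise (seizure, loss of consciousness, or unable to consume treatment) give glucagon, call emergency services and notify study staff.* Carry the same sentence into the guidelines given to participants and companions.

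Leave the discharge and physician-consult sentences exactly as they are, so that who leaves the study does not change, and leave the separate rule in section 10.9.1 alone. Add no new recheck, dose or physician override; the defect does not call for them.

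The cost is a minor amendment, which needs IRB approval under section 14.2, and a handout edit. The primary outcome, randomization and analysis are unchanged.

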6.6.2 Hyperglycemia

If CGM value is >300 mg/dL for 2 hours or >400 mg/dL at any time, check fingerstick BG and ketone level every 60±15 minutes. If unexplained hyperglycemia, evaluate the integrity of the insulin site, consider changing the site and providing a correction bolus as recommended by the bolus calculator. If insulin is given subcutaneous injection rather than through the DiAs, closed-loop control should be suspended for up to four hours unless directed by a study clinician.

6.7 Hotel Session Discharge

Discharge will occur after lunch on Day 3. CGM must be between 80-250 mg/dL with ketones ≤0.6 mmol/L prior to discharge. The study team will answer any remaining questions that the participant may have about using the system at home. After discharge, participants will proceed to the Remote Monitored At-Home Period of the study.

6.8 Other Issues

The participant will be instructed to notify study staff if they experience any issues with the study devices. During the hotel phase, staff will provide hands-on support and troubleshooting training for any device issues. If subcutaneous insulin is needed, the participant will turn off closed-loop mode as instructed by study staff. During the At-Home Period, participants will be instructed to contact the staff on-call in the event of subcutaneous insulin need. If insulin is delivered by any means other than the study pump, the participant will be instructed to turn off closed-loop mode for approximately four hours. This timeframe can be adjusted by the study physician.

The participant will also be asked to alert the study clinical staff for technical issues with the Tandem research pump and/or the DiAs system, including use of the study pump and study CGM (open loop mode) during periods of component disconnections or technical difficulties.

Glucagon will be available at the hotel once the investigational system is in place. All participants will confirm that they have rescue glucagon available at home for the At-Home Period.

Chapter 7: AIDANET+BPS_RL At-Home Period

Visit 7

7.1 AIDANET+BPS_RL use at home

Upon discharge on Day 3 of the hotel period, participants will begin a 7-day/6-night Remote Monitored At-Home stage of the study. Participants will continue to wear the FCL research system as initiated during the hotel period. Participants will be instructed to eat approximately 3 freely chosen meals per day without announcing them to the system. Participants will be instructed to participate in their usual level of physical activity. Participants will complete the study after lunch on overall study Day 9 (Day 7 of the home portion), at which point they will return to use of their usual diabetes care.

Approximately 24-48 hours after initiating the system, the study team will contact the participant via phone/email/text/video to assess adverse events, adverse device effects, and device issues. If the participant chooses, this visit can occur at the clinical site. The study team will verify the following information:

1. Review system use
2. Inquire about any changes to the participant's medical history
3. Inquire about any changes to the participant's medication
4. Review of CGM data
5. Review of hypoglycemic events
6. Review of hyperglycemic events

Any other relevant contacts during the week will be recorded on the CRF and summarized as appropriate (e.g. contact that is not a scheduling or supplies issue will not be recorded).

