7.2 Remote Monitoring

All participants will continue to be remote monitored during the two At-Home Periods of the study, AIDANET and AIDANET + BPS_RL, using the connection between DiAs and DiAs Web Monitoring (DWM) platform at UVA. Study staff may review the AID system data on the DWM platform as needed; in addition, at each site, a licensed medical provider (MD, PA, NP, RN, CDCES) will receive the following automated alerts from the DWM (automated notification system, ANS):

1. CGM > 300 mg/dL for 1 hour.
2. CGM < 70 mg/dL for 20 minutes.
3. CGM < 55 mg/dL at any point.
4. No sensor data for > 1 hour.

The provider on call will contact study participants (e.g., call, text, or video chat) and/or their companion for any of the above CGM alerts which are not resolved within a timely manner. Participants will be asked to manage glycemic extremes per the hyper- hypoglycemia safety protocol.

707 Contact (e.g., phone, text, email, etc.) with the study team will occur as needed. Any relevant
708 contacts will be recorded on the CRF and summarized as appropriate (e.g. contact that is not a
709 scheduling or supplies issue will not be recorded).

710 **7.3 Surveys**

711 All participants will complete the INSPIRE and Technology Acceptance survey at the conclusion
712 of the At-Home study.

713 **7.4 Post-Study Check-In**

714 **Visit 8**

715 Approximately 24-48 hours after the hotel session, the study team will contact the participant via
716 phone/email/text/video to:

- 717 • Ask about any changes to the participant's medical history and medication.
- 718 • Review any hypoglycemic events that are less than 60 mg/dL.
- 719 • Review any hyperglycemic events that are more than 300 mg/dL .
- 720 • Verify that questions have been answered. The study physician or designee will be
721 available for any questions related to insulin adjustments/parameters.

722 The study team may contact the participant for issues related to data collection and equipment
723 issues.

724 **7.5 Early Termination Visit (If Applicable)**

725 Participants will be asked to attend the Post-Study Check-In Visit (visit 8) in the event of a
726 withdrawal or early termination.

727 **7.6 Unscheduled Visits**

728 Participants may have unscheduled visits during the study period if required for additional device
729 training or other unanticipated needs per the study investigator discretion.

Chapter 8: Testing Procedures

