10.7 Reportable Device Issues

All UADEs, ADEs, device complaints, and device malfunctions will be reported irrespective of whether an adverse event occurred, except in the following circumstances.

The following device issues are anticipated and will not be reported but will report as an Adverse Event if the criteria for AE reporting described above are met:

- Component disconnections
- CGM sensors lasting fewer than the number of days expected per CGM labeling
- CGM tape adherence issues
- Pump infusion set occlusion not leading to ketosis
- Battery lifespan deficiency due to inadequate charging or extensive wireless communication
- Intermittent device component disconnections/communication failures not leading to system replacement
- Device issues clearly addressed in the user guide manual that do not require additional troubleshooting
- Skin reactions from CGM sensor placement or pump infusion set placement that do not meet criteria for AE reporting

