12.3 Outcome Measures

The primary outcome will be the CGM-measured time in range (TIR, 70-180 mg/dL) during the 18-hour hotel sessions on AIDANET or AIDANET+BPS_RL (Figure 1). The time periods begin at 6 PM and end at noon on the next day, thereby covering two meals – dinner and breakfast. These

time periods are expected to reflect well any differences, e.g., potential TIR improvement, that can be attributed to the new BPS_RL.

Secondary outcomes from the 18-hour Hotel Sessions of the study (see Figure 1):

Descriptive glycemic analyses for certain efficacy measures recommended by the International Consensus on TIR, to which we contributed, will be tabulated for each subject based on CGM data, including:

- percentage of readings in other ranges, including time below range (TBR, < 70 mg/dl), time above range (TAR, > 180 mg/dl) and time in tight range 70-140 mg/dl;
- mean glucose; glucose variability measured by coefficient of variation;
- percentage of readings <54 mg/dl (i.e., level 2 hypoglycemia)
- percentage of readings >250 and >300 mg/dl (i.e., level 2 hyperglycemia).

Secondary outcomes from the 1-week Home Sessions of the study (see Figure 1):

All CGM-based glycemic metrics computed during the Hotel sessions of the study will be computed during the Home sessions as well. *The last 3 days of each week at home on AIDANET or AIDANET+BPS_RL will be used for the analyses described below.*

We will also observe, record, and tabulate any system errors that would inform us whether system fixes would be needed prior to deployment in a subsequent larger study. We will tabulate technical performance metrics including:

- Malfunctions requiring study team contact and other reported device issues;
- Percent time in closed-loop and any other relevant operational modes;
- Rate of relevant AIDANET+BPS_RL failure events and alarms per 24 hours;

The technical performance, errors, and glycemic analyses will be also split by time of the day: daytime vs. night-time.

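### The rule for logging participant contacts is inverted in four places; followed literally, it drops the contact records behind one descriptive feasibility metric

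*Combined protocol and SAP*

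**What the plan says.** The rule appears in four places in the combined protocol and SAP. In Section 7.1 (home week on AIDANET+BPS_RL) the main clause is "Any other relevant contacts during the week will be recorded on the CRF and summarized as appropriate", followed by a parenthetical example: "contact that is not a scheduling or supplies issue will not be recorded". Section 5.1 (home week on AIDANET) and Chapter 4 (training visit) carry the same parenthesis. Section 7.2, which governs remote monitoring in both home weeks, repeats it: "contacts will be recorded on the CRF and summarized as appropriate (e.g. contact that is not a", continuing to the same ending. No other version of the rule appears elsewhere.

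Section 12.3 lists "Malfunctions requiring study team contact and other reported device issues" as the first of three technical performance metrics. The other two are percent time in closed loop and other operating modes, and the rate of system failure events and alarms per 24 hours. The section introduces them by saying that recorded system errors would inform whether fixes are needed before a larger study.

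Device issues have their own reporting route in Section 10.7: "All UADEs, ADEs, device complaints, and device malfunctions will be reported irrespective of whether an adverse event occurred, except in the following circumstances". The listed exceptions include component disconnections, infusion set occlusions without ketosis, and "Intermittent device component disconnections/communication failures not leading to system replacement". Exempt issues are reported only if they meet the adverse event criteria.

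The plan expects contacts that have nothing to do with scheduling or supplies. Section 7.2 says of unresolved CGM alerts: "The provider on call will contact study participants". Section 6.8 asks participants to tell staff about technical problems with the pump or DiAs, including open-loop use during disconnections.

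**The concern.** The parenthesis contains one negative too many. Its evident purpose is to keep routine logistics off the CRF, but as worded it keeps only routine logistics on it. A clinical or technical call is normally neither scheduling nor supplies, so it is left out.

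This bears on a planned tabulation. The qualifying phrase in the first Section 12.3 metric is that the malfunction required contact with the study team. To count such malfunctions, someone must be able to see that a contact took place and why. If staff follow the parenthesis, that information is not required to be written down. For the device issues that Section 10.7 also exempts, no device-issue report is required either. If some staff follow the wording and others follow the evident intent, capture will be inconsistent. Contacts that were not recorded at the time may be hard to reconstruct later.

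**Working it through.** No arithmetic applies. The plan gives no figure for contacts or malfunctions, so the check is to apply the rule to typical contacts and see which other route, if any, would capture each one.

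**Step 1. Apply the rule literally.** The contacts are illustrations, not estimates of frequency.

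| Contact | Main clause (relevant contacts recorded) | Parenthesis as written |
|---|---|---|
| Call about a DiAs-pump disconnection | recorded | not recorded |
| Call about repeated low glucose | recorded | not recorded |
| On-call provider contacts a participant about missing sensor data (Section 7.2 alert) | recorded | not recorded |
| Request for more infusion sets | not needed | not excluded |

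The parenthesis reverses the main clause on the first three rows and fails to exclude the fourth. Removing its first negative makes the two agree on all four rows.

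**Step 2. Look for another route for each kind of event.**

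- *Malfunctions and complaints not exempt under Section 10.7.* These are reported as device issues whether or not an adverse event occurred, and Section 10.8 asks for prompt reporting. They are captured without the contact CRF.
- *Issues exempt under Section 10.7* (component disconnections, communication failures without system replacement, occlusions without ketosis). No device-issue report is required unless adverse event criteria are met. If the call is also left off the CRF, neither form is required to hold it.
- *Issues covered in the user guide.* Section 10.7 exempts these only when no additional troubleshooting is needed. One that does need further troubleshooting is not exempt on this ground, so this exemption contributes little to the gap.
- *Low or high glucose.* These appear in the CGM data and trigger the Section 7.2 alerts. They are not malfunctions in themselves, so their loss affects the summary of contacts rather than the Section 12.3 malfunction count.

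**Step 3. Separate the event from the contact.** Section 2.7 has device data captured in real time by the remote monitoring server and downloaded after the home visits. Section 12.7 removes CGM data around recorded occlusions and after pump/DiAs communication interruptions, which presupposes that these are logged. Sections 5.1 and 7.1 schedule a contact about 24-48 hours after the system is started "to assess adverse events, adverse device effects, and device issues". An exempt disconnection may therefore still be visible as an event. Nothing in these routes, as described, says that server data will show whether the event required study-team contact, and the check-in falls early in each week.

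**Step 4. Locate the residual gap.** It is the record that an issue required contact, mainly for the Section 10.7 exempt classes, during the training visit and the two home weeks. Chapter 6 does not state the rule for the hotel sessions.

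**The case against.** The best defence is that the intent is obvious. The operative clause says relevant contacts are recorded, and the inverted text is only an example attached to it. The documents do not show that staff would apply the example literally. That is fair, and a drafting slip is the likely explanation. What remains is that the same wording appears in all four places, with no correct version to overrule it.

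Second, Section 12.3 speaks of malfunctions requiring contact together with other reported device issues, which suggests that the source is the Section 10.7 reports rather than the contact CRF. No section names the source. If it is Section 10.7, the exempt classes fall out of the count whatever the contact rule says, so the source should be stated.

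Two stronger readings are tempting, and the documents support neither.

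- *A reader might infer that the malfunction outcome is lost.* It is not. Non-exempt malfunctions are still reported, device issues are asked about at the check-in, device data reach the server in real time, and Section 12.3 separately tabulates system errors, time in closed loop, and failure and alarm rates.
- *A reader might infer that the new algorithm will look more trouble-free than AIDANET.* The rule is the same in Sections 5.1 and 7.1, so it does not by itself favour either algorithm. It could lower the absolute count of malfunctions that required contact, in both weeks.

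**Conclusion.** The point holds as a minor one. The inversion is certain, because the wording can be read at all four places and it contradicts its own main clause. Its consequence is limited to one descriptive feasibility metric, and within that metric mainly to the device-issue classes exempt under Section 10.7.

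The primary outcome (time in range in the randomized hotel sessions), the sample size and the glycemic analyses do not depend on it. Nor do the success criteria in Section 12.6, which are critical system errors plus time in, below and above range and contain no contact count.

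The conclusion assumes that at least some staff would follow the parenthesis as written, and that the contact CRF is a source for the first Section 12.3 metric. The documents settle neither. They also give no contact or malfunction rate, so no effect size can be attached.

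**What to change.** In Chapter 4 and Sections 5.1, 7.1 and 7.2, replace the parenthesis with: *(contacts that concern only scheduling or supplies will not be recorded)*. All four places need the change; correcting Section 7.1 alone would leave the other three contradicting it.

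In Section 12.3, name the contact CRF as a source for the metric on malfunctions that required study-team contact.

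The cost is one parenthesis corrected four times and one phrase added. No new visit, procedure or staff is needed.
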